#### **Exposure to any teratogenic medications (including steroids):**

Information on co-medication will be obtained from Prescription Registers (FIN, SWE, NOR). The medications included consist of high-risk medicines during pregnancy according to the Swedish Catalogue of Approved Drugs (FASS) (Berglund 1984, FASS 1993). This classification comprises 4 separate categories (A, B, C, D): A includes the safest drugs; B is divided into 3 subgroups (B1, B2, B3); and C and D categories are used for drugs which may have different risks for the foetus depending on the evidence on which the risk is based. In this study, drugs from categories C and D will be included as potentially teratogenic drugs or teratogenic drugs (see Annex 3 for the classification of teratogenic medications and for a detailed list of specific ATC codes). From these medications a binary variable will be created to indicate if the mother has been exposed to any teratogenic medications (including steroids) before or during pregnancy (Yes, No). Pregnancies are considered unexposed to an MSDMD if the medication has not been used within 3 months prior to LMP or during pregnancy (except for mitoxantrone and cladribine, for which 6 months must be allowed).

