### 9.4 Variables

**Exposures:** Maternal MS and related medication exposure before and during pregnancy are the basis of the exposure status of the study subjects in this study.

Pregnancies are considered unexposed if no MSDMDs of interest have been used within three months (except six months for mitoxantrone and cladribine) prior to LMP or during pregnancy. As the maximum reimbursable amount per purchase is the supply for three months of treatment, a pregnancy is defined as unexposed to MSDMDs if there are no purchases of MSDMDs within six months (except nine months for mitoxantrone and cladribine) prior to LMP or during pregnancy. Otherwise a pregnancy is defined as exposed to MSDMDs. Similarly, a pregnancy is defined as unexposed to IFN- $\beta$  if there have been no purchases of IFN- $\beta$  containing medications within six months prior to LMP or during pregnancy and otherwise a pregnancy is defined as exposed to IFN- $\beta$ .

The following MSDMDs and their ATC codes are included in this study: IFN- $\beta$ -1a (L03AB07), IFN- $\beta$ -1b (L03AB08), Peg IFN- $\beta$ -1-a (L03AB13), human normal immunoglobulin (J06BA02), cyclophosphamide (L01AA01), methotrexate (L01BA01, L04AX03), cladribine (L01BB04), mitoxantrone (L01DB07), alemtuzumab (L01XC04), glatiramer acetate (Copaxone®) (L03AX13), leflunomide (L04AA13), natalizumab (L04AA23), fingolimod (L04AA27), teriflunomide (L04AA31), azathioprine (L04AX01), dimethyl fumarate (N07XX09).

**Table 3: More detailed information on individual MSDMD agents, including information on availability and reimbursement in FIN, SWE and NOR.**

MSDMD agent	ATC code	Reimbursed in FIN in Jan 2015 (yes / no) 	Marketing authorisation date			Administration in hospital only 
			FIN	SWE	NOR	
IFN- $\beta$ natural	L03AB02		no	no	no	
IFN- $\beta$ -1-a	Avonex ®	yes	13.3.1997	13.3.1997	5.7.2002	no
	Rebif ®		4.5.1998	4.5.1998	19.8.2003	no
IFN- $\beta$ -1-b	Betaferon ®	yes	30.11.1995	30.11.1995	1.9.2006	no
	Extavia ®		20.5.2008	20.5.2008	20.5.2008	no
Peg IFN- $\beta$ -1-a	Plegridy ®	yes	18.7.2014	18.7.2014	18.7.2014	no
intravenous immunoglobulin	J06BA02	no	16.10.1991	10.10.1981	9.10.1996	yes
cyclophosphamide	L01AA01	no	4.6.1986	28.4.1959	6.4.1959	injection yes tablet no
methotrexate	L01BA01	yes  / no 	25.2.1981	23.6.1964	14.4.1971	tablet no
	L04AX03					infusion yes injection yes/no 

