The estimated background prevalence for the composite endpoint of serious adverse pregnancy outcome, consisting of TOPFAs, live births with MCA and all stillbirths, was 6.5% (personal communication with [name], THL, 15 May 2014) and 7.3% (= 24/331, based on the feasibility study in Finland, cf. Annex 1) in women with MS unexposed to IFN- $\beta$  (regardless of exposure to other MSDMDs) and unexposed to any MSDMD, respectively. Because these numbers best correspond to the study setting, they were taken as the most relevant baseline prevalences of serious adverse pregnancy outcomes in the sample size calculations. Lower outcome prevalences were investigated to test how sensitive the findings of minimum detectable effect sizes are to these assumptions. For comparison, in the Finnish feasibility study the prevalence of serious adverse outcomes was 3.7% = (38384/1031778) among all women, and according to EUROCAT 2015, the prevalence of malformation outcome among all women in the EU is 2.6%. The anticipated sample sizes in study cohorts 1-6 are:

- Cohort 1: 294 (80% of 368) for MS pregnancies exposed only to IFN- $\beta$ .
- Cohort 2: 368 (22% of 1671) for MS pregnancies exposed to IFN- $\beta$  regardless of exposure to other MSDMDs.
- Cohort 3: 1270 (76% of 1671) for MS pregnancies unexposed to any MSDMD.
- Cohort 4: 1303 (78% of 1671) for MS pregnancies unexposed to IFN- $\beta$ .
- Cohort 5: 33 (Cohort 4 size – Cohort 3 size = 1303 – 1270 = 33) for MS pregnancies exposed to MSDMDs except IFN- $\beta$  or glatiramer acetate (Copaxone®) or dimethyl fumarate (Tecfidera®).
- Cohort 6: Approximately 2.9 Million pregnancies for women from the general population in FIN, SWE and NOR without MS diagnosis based on the based on the feasibility study (cf. Annex 1).

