### 9.7.3 Analysis of primary objectives

With regard to objective #1, the descriptive statistics including the number of events (n) and prevalence (%) will be presented for each pregnancy outcome (i.e. serious adverse pregnancy outcome, elective TOPFA, MCA, stillbirth, and live birth) in each study cohort separately and also for the whole study population. Information on live births, stillbirths and TOPFAs will be included in the analyses of MCA, as approximately 10% of MCAs are detected in foetuses of TOPFA.

With regard to objective #2, the prevalence of the serious adverse pregnancy outcomes will be compared between the study cohorts using log-binomial regression. Two models, base and adjusted, will be used in these comparisons. The base model will be adjusted for the following design variables and *a priori* likely confounders: country, year of pregnancy outcome, maternal age at LMP, number of previous pregnancies, any chronic diseases, and exposure to any teratogenic medications including steroids.

The adjusted model will be built using a variable selection procedure (Bursac et al. 2008). Candidate covariates for the adjusted model will be those in the base model and the following additional ones: university hospital district, pre-pregnancy weight, pre-pregnancy BMI, number of previous abortions, smoking status during pregnancy, number of foetuses in pregnancy (single vs. multiple), time since MS diagnosis and duration of MS treatment as available in the data sources. Variable selection starts by applying first the unadjusted model and proceeds as follows:

1. Each candidate covariate will be considered a potential confounder if the univariate association between the covariate and the serious adverse pregnancy outcome, tested with the Wald test for logistic regression with *P*-value cut-point of 0.25.
2. All candidate covariates identified as potential confounders in step 1 will be added simultaneously to the model. After this, additional covariates not identified as potential confounders in step 1 will be added to the model one at a time and the model fit comparing each null vs alternative model will be assessed by the likelihood-ratio test. Variables in the alternate model will be retained at a likelihood ratio test of *P*-value <0.1.

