C	
Medicinal products, which by their pharmacological effects have caused or must be suspected of causing, disturbances in the reproductive process that may involve risk to the foetus without being directly teratogenic. If experimental studies in animals have indicated an increased occurrence of foetal injuries or other disturbances of the reproductive process of uncertain insignificance in humans, these findings are to be stated for drugs in this category.

D	
Medicinal products, which have caused an increased incidence of foetal malformations or other permanent damage in humans or which, on the basis of e.g. reproduction toxicity studies, must be suspected of doing so. This category comprises drugs with primary teratogenic effects that may directly or indirectly have a harmful effect on the foetus.

[figure not shown]
In this study, the following drugs (ATC codes) from categories C and D will be included in this study as potentially teratogenic drugs or teratogenic drugs.

	ATC codes						
Potentially teratogenic drugs – risk category C	A01AB11	A01AC01	A02BC02	A03AB02	A03FA01	A04AA03	A04AD12
	A05AA02	A07DA03	A07EA02	A07EA06	A10BB01	A10BB07	A10BB12
	A10BG02	A10BG03	A10BH01	A10BX02	A10BX03	A11HA30	B01AC06
	B01AC11	B01AC30	B01AD02	B01AD07	B01AD11	B01AE07	B03XA01
	C01BC03	C01BC04	C01BD01	C01BD05	C01CA04	C01CX08	C01EA01
	C02AC05	C03AA03	C03BA11	C03CA01	C03EA01	C04AD03	C07AA03
	C07AA05	C07AA07	C07AB02	C07AB03	C07AB05	C07AB07	C07AB09
	C07AG01	C07AG02	C07FB02	C08CA01	C08CA02	C08CA03	C08CA05
	C08CA06	C08CA07	C08CA13	C08DA01	C08DB01	C08DB01	C10AA03
	C10AA04	C10AA07	C10AB02	C07AB09	C07AG01	C07AG02	C10AB04
	C10AB05	D01AA02	D01AC07	D01AC08	D01AE16	D05AX03	D05AX52
	D06BB03	D06BB04	D07AB01	D07AB02	D07AB08	D07AC01	D07AC03
	D07AC13	D07AD01	D07BC01	D07CC01	D07XC01	D08AG02	D10AD01
	D10AD03	D11AH01	D11AX01	D11AX18	G01AF08	G02AB01	G02BB01
	G02CB03	G03AA11	G03AA12	G03AA13	G03AB03	G03AB05	G03AB06
	G03AC01	G03AC03	G03AC08	G03AC09	G03CX01	G03DA02	G03FA01
	G03FA12	G03FA17	G03FB05	G03FB06	G03GA01	G03AA07	G03AA09
	G03AA10	G03GA01	G03GB02	G03HB01	H01CA02	H01CB02	H01CB03
	H01CC02	H02AA02	H02AB01	H02AB02	H02AB04	H02AB06	H02AB07
	H02AB08	H03BB01	H05AA02	J01CA08	J01EA01	J01EE01	J01EE02
	J01FA09	J01FA15	J01GB01	J01MA01	J01MA02	J01MA06	J01MA12
	J01MA14	J01XC01	J01XE01	J01XX08	J02AB02	J02AC01	J02AC02
	J02AC03	J02AX04	J04AB02	J04AB04	J05AB01	J05AB11	J05AE02
	J05AE03	J05AE07	J05AF01	J05AF05	J05AF06	J05AF08	J05AR01
	J07BA02	J07BK01	L01XE01	L01XE06	L01XX19	L01XX23	L02AB01

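### The teratogenic-medication covariate in the base model includes the study drug's own ATC codes, so cohort 1 is coded Yes by construction

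*Protocol*

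**What the plan says.** Section 9.4 defines the exposure by ATC code. The sentence opening "The following MSDMDs and their ATC codes are included in this study" lists IFN-beta-1a (L03AB07), IFN-beta-1b (L03AB08) and peginterferon beta-1a (L03AB13). It also lists the other MS disease-modifying drugs (MSDMDs), among them leflunomide (L04AA13), azathioprine (L04AX01) and methotrexate (L01BA01, L04AX03).

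The same section defines a covariate for teratogenic medication, including steroids: "From these medications a binary variable will be created to indicate if the mother has been exposed to any teratogenic medications". It sends the reader to Annex 3 for the codes. Annex 3 states that "the following drugs (ATC codes) from categories C and D will be included in this study as potentially teratogenic drugs or teratogenic drugs". Its category D list contains L03AB07, L03AB08, L04AA13, L04AX01 and L04AX03.

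Section 9.7.3 says prevalences are "compared between the study cohorts using log-binomial regression", and its base model always includes "number of previous pregnancies, any chronic diseases, and exposure to any teratogenic medications including steroids" alongside country, year and maternal age. The covariate is also a candidate for the adjusted model and a stratifier in objective 5.

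**The concern.** A covariate meant to capture other harmful drugs has the exposure built into it. For a cohort 1 woman on L03AB07 or L03AB08, the Yes says nothing about what else she took. For a cohort 3 woman, Yes means real use of another category C or D drug. Three things follow.

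- The IFN-beta coefficient becomes a contrast between all of cohort 1 and the medicated part of cohort 3. If the listed drugs raise the risk of the composite outcome, the RR is pulled down, towards false reassurance in a safety study.
- Genuine co-medication within cohort 1 is no longer measured, so the confounding the covariate was meant to control is not controlled.
- Cohort 3 women coded No stop informing the exposure contrast, except through the other covariates, so precision falls.

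The comparison of cohort 2 with cohort 3 under objective 3 is analysed in the same way and inherits the problem. In objective 5 the No stratum is nearly empty for cohorts 1 and 2.

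**Working it through.** **Inputs from the protocol (section 9.5).** Cohort 1: n=294. Cohort 3: n=1270. Prevalence in cohort 3: 7.3% (24/331). Power 80%, two-sided 5%.

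**Assumptions, not in the protocol.** t is the share with genuine category C or D co-medication, and R is its risk ratio for the outcome. Both are shown as ranges.

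**1. Reproduce the planned figure.** The method is the two-proportion normal approximation with pooled null variance and unequal groups, which is what bpower computes. With p1 = RR × p3 and p̄ the size-weighted mean, power is Φ[(p1 − p3 − 1.96·s0)/s1]. Here s0² = p̄(1−p̄)(1/294 + 1/n3) and s1² = p1(1−p1)/294 + p3(1−p3)/n3. With n3=1270, solving for 80% power gives RR 1.717 at 7.3% and 1.720 at 24/331. The stated 1.72 is confirmed.

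**2. What the contaminated model estimates.** Let p0 be the risk in cohort 3 women coded No and θ the true IFN-beta RR.

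| Cell | Risk |
|---|---|
| Cohort 3, No | p0 |
| Cohort 3, Yes | p0·R |
| Cohort 1, Yes (everyone) | p0·θ·[1 + t(R−1)] |
| Cohort 1, No | empty |

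The covariate coefficient is set by the two cohort 3 cells. The IFN-beta coefficient is then the log of the third row over the second:

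fitted RR = θ × [1 + t(R−1)]/R.

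For the bias, only the share in cohort 1 matters. The share in cohort 3 determines how many comparators remain.

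**3. Size of the bias factor.**

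| t | R=1 | R=1.1 | R=1.25 | R=1.5 | R=2 |
|---|---|---|---|---|---|
| 0.1 | 1.00 | 0.92 | 0.82 | 0.70 | 0.55 |
| 0.3 | 1.00 | 0.94 | 0.86 | 0.77 | 0.65 |
| 0.5 | 1.00 | 0.95 | 0.90 | 0.83 | 0.75 |
| 0.8 | 1.00 | 0.98 | 0.96 | 0.93 | 0.90 |

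Example: with t=0.3 and R=1.5, a true RR of 1.72 is estimated as 1.72 × 0.767 = 1.32. Log-binomial fits to expected counts give the same values. A 400-replicate simulation (Poisson regression with robust variance, 294 vs 1270, t=0.3, R=1.5, true RR 1.30) gave a mean RR of 1.00 with the covariate as listed and 1.29 with a clean covariate. The closed form predicts 1.30 × 0.767 = 1.00. The standard error of the log RR was 0.240 against 0.205, or 17% larger.

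**4. Loss of precision when there is no bias (R=1).** The comparator shrinks to t × 1270, with t now the cohort 3 share. The formula in step 1 at 7.3% gives:

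| t | Comparators | Minimum detectable RR | Power at RR 1.72 |
|---|---|---|---|
| all (clean list) | 1270 | 1.72 | 80% |
| 0.8 | 1016 | 1.74 | 78% |
| 0.5 | 635 | 1.80 | 72% |
| 0.3 | 381 | 1.91 | 63% |
| 0.1 | 127 | 2.36 | 34% |

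**5. Bias and precision together.** The 1.91 belongs to R=1 only. With t=0.3, R=1.5 and cohort 3 held at 7.3% overall, the medicated women have prevalence 0.073 × 1.5/1.15 = 9.5%. The formula with 294 vs 381 then gives a detectable fitted RR of 1.77. Because the fitted RR is the true one times 0.767, the true RR would have to be about 1.77/0.767 = 2.3.

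**The case against.** The strongest reply is that the intent is visible. Section 9.4 introduces the variable as co-medication and defines MSDMD exposure separately, and section 9.7 announces a statistical analysis plan in which derivations would be coded. On this view, the code list was simply not cleaned. That may well be how it arose, but the word is a hint and the code list is the rule. The paragraph even ends with a rule on when a pregnancy counts as unexposed to an MSDMD, which reads as if those drugs belong to the variable.

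Several narrower points stand:

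- The model remains estimable. The fault is a shifted contrast and lost precision.
- The bias is downward only if R exceeds 1. Category C makes up most of the list and is defined as not directly teratogenic, so R may be near 1. At R=1.1 the factor is 0.92 to 0.98 for t from 0.1 to 0.8.
- Coding is not Yes for literally everyone. Peginterferon (L03AB13, authorised July 2014) is not on the list. The covariate's look-back length is not stated, so a window shorter than the six-month purchase window for IFN-beta would leave some cohort 1 pregnancies at No.
- The three non-interferon codes cannot affect cohort 1 against cohort 3 within the exposure window. Against cohort 4 they concern at most 33 of 1303 pregnancies (1303 − 1270).
- In the adjusted model the covariate is only a candidate. Objective 1 is untouched, and objective 5 is descriptive.

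None of this removes the fault from the base model of the primary comparisons.

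**Conclusion.** The concern holds and should be corrected before analysis. That L03AB07 and L03AB08 sit in a covariate forced into the base model follows from the protocol's text alone and needs no assumption. The size does need assumptions. With t from 0.1 to 0.5 and R from 1.25 to 2, the base-model RR is multiplied by 0.55 to 0.90. With R=1 there is no bias, but the minimum detectable RR rises from 1.72 to between 1.74 and 2.36 for t from 0.8 down to 0.1. A small co-medication share makes both effects worse. These figures assume that the covariate window covers the IFN-beta exposure window and that few cohort 1 women used peginterferon only.

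**What to change.** In section 9.4, state that the covariate measures co-medication other than the MSDMDs. For building it, delete from Annex 3 every code in the section 9.4 MSDMD list: L03AB07, L03AB08, L04AA13, L04AX01 and L04AX03. Use the cleaned variable in the base model, the adjusted model and the objective 5 strata.

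Two clarifications belong in the same edit. First, state the covariate's look-back length, which is now left open. Second, say that in the comparison with cohort 4 the other MSDMDs are deliberately not adjusted for through this variable, because that cohort is defined regardless of their use.

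The cost is a few sentences in section 9.4 and five codes in Annex 3. No new data are needed, and the planned figure of 1.72 then rests again on all 1270 cohort 3 pregnancies.

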## 7 Rationale and background

MS is the most common chronic neurologic disability in young adult females of childbearing age (Baird & Dalton 2013). Women with MS are confronted with questions relating to pregnancy and pharmacological MS therapy. It is commonly understood that MS relapses are fewer during pregnancy, but also that medication taken before conception or in early pregnancy could negatively affect the outcome of the pregnancy. Experience with exposure to IFN- $\beta$  products during pregnancy has shown no clear association of adverse outcomes such as low birth weight (LBW), congenital anomaly or spontaneous abortion (Lu et al. 2012). However, it is contraindicated to initiate treatment with IFN- $\beta$  products during pregnancy. It is also recommended that if a woman becomes pregnant during treatment, she should be informed of the potential hazards and discontinuation of therapy should be considered. In patients with a high relapse rate before treatment start, the risk of a severe relapse following discontinuation of IFN- $\beta$  in the event of pregnancy should be weighed against a possible increased risk of spontaneous abortion. There are little data on newer MSDMD substances (e.g. fingolimod) (Lu et al. 2012).

This study addresses a request from the European Medicines Agency's CHMP to identify pregnancy outcomes in the MS population unexposed to IFN- $\beta$  products for comparison with the ongoing European IFN- $\beta$  Pregnancy Registry sponsored by the four European MAHs of IFN- $\beta$ s.

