### 9.2.4 Follow-up time

The cohort entry date (i.e. index date) is the date of LMP. This date is considered as the beginning of the pregnancy. The pregnancies are followed until induced abortion or birth. The births are followed-up for a maximum of 12 months for registration of MCAs (see section 9.2.3 Study period). Information on LMP, or gestational age, is not available for ectopic pregnancies or spontaneous abortions. The date of hospitalisation due to these outcomes will be used as a proxy of index date for these outcomes.

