## Any chronic diseases:

- Information on chronic diseases available from the DPP (FIN), MBR (FIN, SWE, NOR), MS Register, Patient Register (SWE, NOR), Prescription Register (FIN, SWE, NOR) will be used to define pharmacological treatment for comorbidities. The comorbidities listed in Table 4 existing before, or during pregnancy will be identified based on diagnoses or specific medications for chronic diseases. These represent the most common chronic diseases among women who have been pregnant (information source the DPP, years 1996-2010). Information is based on pre-pregnancy diagnoses. From these comorbidities a binary variable will be created to indicate if the mother has had any chronic diseases before or during pregnancy (Yes, No). Lifetime pre-pregnancy diagnoses are included from the time period included in the data sources.

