**Table 4: List of chronic diseases diagnosed before LMP and during pregnancy.**

Comorbidities	ICD-10	Proportion of women with the disease among parturient (%) in Finland 1996-2010 
Asthma and related conditions	E84.0, J41–J45, P27.1	2.77
Hypothyroidism (thyroid insufficiency)	C73, E03, E89.0	0.82
Epilepsy	C71, G40, G41	0.80
Rheumatoid arthritis and related conditions	A04.6, A39.8, A50.5, D76.0, D76.3, H20.1, H30, I33.0, J84, K50.9, K51.9, K73.2, K74.3, K83.0, L40.5, M02, M05, M06, M08, M13.9, M30–M35, M45, M46.1, M46.9, M94.1, N03, Q44.2	0.61
Diabetes Mellitus (type I and type II will be considered separately)	E10–E14, E89.1	0.52
Colitis Ulcerosa, Crohn's disease	K50, K51	0.50
Hypertensive diseases	I10–I13, I15, I27.0	0.38
Severe psychosis and other severe mental disorders and related conditions	A52.1, A69.2, A81.0, B22.0, B56.9, B57.2, E01.8, E03.9, E52, E53.8, E75.6, E83.0, E83.5, F01, F03, F06.0–F06.3, F20–F25, F28, F29, F30.1, F30.2, F31, F32.3, F33.3, F84, G10, G20, G30.0, G30.1, G30.8, G30.9, G31.0, G35, G40.9, M30.0, M32.8	0.32
Leukaemia and related conditions	C81–C85, C88, C90–C96, D45–D47, D72.1, D75	0.06
Hypercholesterolemia and mixed hyperlipidemia	E78.0, E78.2	0.05
Hypogonadism	E28.3, E29.1, E89.4, E89.5, Q96, Q98	0.04
Hypertensive heart disease with heart failure and related conditions	I11.0, I13, I50, I97.1, P29.0	0.04
Chronic arrhythmia of the heart	I47–I49	0.04
Glaucoma	H40	0.03
Pernicious anemia and deficiency of specified B group vitamins	C16, D51, E53.8	0.03

Comorbidities	ICD-10	Proportion of women with the disease among parturient (%) in Finland 1996-2010 
Hypothyroidism parathyroid gland, chronic (parathyroid insufficiency)	E20, E31.0, E89.2	0.02
Deficiency of coagulation, hemophilia	D66, D67, D68.0–D68.2	0.01
Myasthenia gravis	G70.0	0.01
Maternal pregnancy-related disorders	O10-O29	not available from DPP
Other malignancies	C00-C80	not available

Lahesmaa-Korpinen et al. 2014

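### The base-model flag for teratogenic medication runs to the end of pregnancy, so it depends on pregnancy length and can bias the IFN-β RR if purchasing differs between cohorts; the chronic-disease window is unresolved

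*Protocol*

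**What the plan says.** **Drug covariate.** Protocol section 9.4 turns the Annex 3 list into a Yes/No variable to "indicate if the mother has been exposed to any teratogenic medications (including steroids) before or during pregnancy (Yes, No". It gives neither a gestational cut-off nor a start of look-back. The three- and six-month rule that closes the paragraph concerns MSDMDs, not this covariate. Section 9.7.1 repeats the open window.

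**Chronic-disease covariate.** The same section builds a variable to "indicate if the mother has had any chronic diseases before or during pregnancy (Yes, No", but just before that it states: "Information is based on pre-pregnancy diagnoses". The title of Table 4 reads "List of chronic diseases diagnosed before LMP and during pregnancy", and its rows include "Maternal pregnancy-related disorders" (O10-O29).

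**Use in the model.** The base model in section 9.7.3 contains "number of previous pregnancies, any chronic diseases, and exposure to any teratogenic medications including steroids", treated as confounders chosen in advance. The abstract applies the same baseline adjustment to pregnancy outcomes generally.

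**Time zero.** Section 9.2.4 sets the index date at LMP. For spontaneous abortion and ectopic pregnancy it says: "The date of hospitalisation due to these outcomes will be used as a proxy of index date for these outcomes". Section 9.9 does estimate LMP for these two outcomes (diagnosis date minus 9 or 8 weeks), but only to obtain maternal age.

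**The concern.** A baseline confounder should be known at time zero. This one goes on accumulating until the outcome stops it.

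- **Observation time is set by the outcome.** A live birth has some 40 weeks in which a purchase can turn the flag to Yes, and a termination has far fewer. A spontaneous abortion or ectopic pregnancy, indexed at the hospital date, has no time during pregnancy at all.
- **The flag can include treatment that follows exposure.** Section 7 names "the risk of a severe relapse following discontinuation of IFN"-β, and systemic steroids (the H02AB codes in Annex 3, category C) set the flag to Yes. If IFN-β or stopping it leads to such purchases, adjustment removes part of the effect under study.
- **Two listed codes can record the outcome itself.** Annex 3, category D, includes G03XB01 and A02BB01, which in the ATC system are mifepristone and misoprostol. If dispensed at a pharmacy for a termination, they enter an outcome as a covariate.

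At stake are the adjusted RRs for the primary composite and, more directly, for spontaneous abortion and ectopic pregnancy in objective 4.

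**Working it through.** **1. The plan's own figure.** With 294 in cohort 1, 1270 in cohort 3, 7.3% background risk and two-sided 5%, a pooled-variance two-proportion calculation gives 80% power at RR 1.717 (stated: 1.72). The study-size figures do not depend on this point. For scale, SE(log RR) = √[0.927/(294×0.073) + 0.927/(1270×0.073)] = 0.23, so a 95% interval spans a factor of exp(1.96×0.23) ≈ 1.57 each way.

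**2. How the flag depends on pregnancy length.** Assumed, not in the documents: weekly purchase hazard h of 0.01 or 0.03; 4 weeks observed before LMP; TOPFA at 18 weeks, other terminations at 9, births at 39; hazard multiplied by k in cohort 1.

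P(Yes) = 1 − exp[−k·h·(4 + weeks)]

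At h = 0.03 and k = 1:
- other termination: 1 − exp(−0.39) = 0.32
- TOPFA: 1 − exp(−0.66) = 0.48
- birth: 1 − exp(−1.29) = 0.72

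One purchasing rate gives three values of a covariate meant to describe baseline.

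**3. Composite, true RR 1.00.** A log-binomial model with exposure and flag is fitted to expected counts (294 and 1270, risk 7.3% in both). TOPFA is 10, 30 or 50% of events. Terminations are 0, 10 or 20% of non-events; the upper value is the abortion prevalence in the notes to Table 5.

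| k | RR of the flag itself | adjusted IFN-β RR |
|---|---|---|
| 1 | 0.61 to 1.27 | 1.00 throughout |
| 0.5 | 0.62 to 1.24 | 0.88 to 1.05 |
| 2 | 0.58 to 1.30 | 0.95 to 1.14 |

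Both extremes, 0.88 and 1.14, need TOPFA at 50% of events, no short non-events and h = 0.03. With TOPFA at 10% and no short non-events the range is 0.975 to 1.025. The direction reverses when short pregnancies are mostly non-event terminations, which Table 6 keeps in the denominator.

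**4. Spontaneous abortion, true RR 1.00.** Assumed: 12% risk; 15 or 30% Yes before the index date; 20 or 40% with a first purchase over 40 weeks; 0 or 9 weeks observed for losses and 40 for all others; k applied to purchases during pregnancy only, or also to those before.

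P(Yes) = 1 − exp[−(H_before + H_during × weeks/40)], with H = −ln(1 − proportion)

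- k = 1: adjusted RR 1.00, although the flag's own RR is 0.22 to 0.67
- k = 1.25: 1.01 to 1.10
- k = 1.5: 1.02 to 1.20

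The 1.20 needs 0 weeks for losses, 15% before, 40% during, and k = 1.5 on both parts. With 9 weeks the maximum is 1.15. If 20% of non-events are also terminations at 9 weeks, it is 1.11.

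**5. Treatment after exposure.** Suppose a purchase in pregnancy multiplies composite risk by r and is made by p1 of cohort 1 and p0 of the comparator. The total RR through this path is [1 + (r−1)p1]/[1 + (r−1)p0]. With r = 1.3, p0 = 0.20, p1 = 0.30 it is 1.09/1.06 = 1.03. With r = 2, p0 = 0.30, p1 = 0.45 it is 1.45/1.30 = 1.12. Adjustment returns 1.00 in both. All these inputs are assumed.

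**6. Chronic disease.** No arithmetic is needed. Two statements in one paragraph give different windows, and the title and last rows of Table 4 side with the later one.

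**The case against.** The strongest reply is that dependence on pregnancy length alone biases nothing. Steps 3 and 4 confirm it: with equal purchasing the RR stays at 1.00. Bias needs a purchasing difference between cohorts, which the documents do not quantify. Against a 1.57-fold confidence factor, most of the composite shifts are small. This stands, and it limits the claim to what can happen.

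The relapse route is also weaker than section 7 read selectively suggests. That section says relapses are fewer in pregnancy, and section 9.7.6 notes that steroids may be infused in hospital, where the prescription registers do not see them. IFN-β purchases also count to the end of pregnancy, so a listed purchase need not follow exposure. The termination drugs are a code-list defect rather than a window defect. They matter only if dispensed at a pharmacy, and Sweden contributes no terminations. All of this stands.

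A reader might infer that both covariates are fixed at the end of pregnancy. The documents support that only for the drug flag. A reader might also infer that losses have no observation time at all. Because no look-back start is given, purchases in the weeks before the hospital date may count as before pregnancy.

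On cost, the Finnish DPP holds purchases from only one month before pregnancy. That does not block a pre-LMP window. Section 9.4 already needs six months of MSDMD purchases before LMP, and Table 2 lists the National Prescription Register. Nor does any planned analysis close the gap: the first-trimester analysis in section 9.7.6 concerns exposure timing for MCA and does not mention covariates.

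**Conclusion.** The point holds for the drug covariate. It is measured after time zero, for a period that the outcome determines, and it is fixed in the base model. Adjusting for it can bias the IFN-β RR in either direction if listed-drug purchasing differs between cohorts, and not otherwise. The illustrative ranges are 0.88 to 1.14 for the composite when cohort 1 buys at half or twice the rate, and 1.01 to 1.20 for spontaneous abortion at 1.25 to 1.5 times the rate, with 1.20 an extreme corner. They rest on the assumed hazards, gestational lengths and outcome mix in the working. The spontaneous-abortion range is upward only because cohort 1 was assumed to buy more. The documents do not support saying that the RR is biased, or by how much.

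For chronic disease the finding is an internal contradiction to reconcile, not a settled end-of-pregnancy window. The plan should be changed, but the study does not fail on this.

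**What to change.** - **Sections 9.4, 9.7.1 and 9.7.3:** define the drug covariate over one fixed look-back ending at LMP for every pregnancy, for example the six months already used for MSDMD purchases. Take it from the prescription registers, not from the one-month DPP window.
- **Spontaneous abortion and ectopic pregnancy:** end the look-back at the estimated LMP of section 9.9.
- **Annex 3:** remove G03XB01 and A02BB01 from the covariate list. This still matters for the sensitivity analysis below, whose window extends past LMP.
- **Chronic disease:** reconcile the paragraph and Table 4 to pre-LMP diagnoses.
- **Purchases during pregnancy:** describe them separately. Add a sensitivity analysis of the composite and MCA that adjusts for listed drugs bought up to the end of the first trimester.

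The cost is wording and one changed derivation, using registers already named in Table 2. The downside is that co-medication first bought after LMP leaves the main model and appears only in the sensitivity analysis. Closing the window does not deal with L03AB07 and L03AB08, the IFN-β codes that also stand in category D. That is a separate matter, best settled in the same edit.
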